Sponsor	The sponsor is the party that commissions the organisation or performance of the research, for example a pharmaceutical company, academic hospital, scientific organisation or investigator. A party that provides funding for a study but does not commission it is not regarded as the sponsor, but referred to as a subsidising party.
SUSAR	Suspected Unexpected Serious Adverse Reaction
SPSS	Statistical Package for the Social Sciences
WISC	Wechsler Intelligence Scale for Children
WMO	Medical Research Involving Human Subjects Act; in Dutch: Wet Medisch-wetenschappelijk Onderzoek met Mensen
WPPSI	Wechsler Preschool and Primary Scale of Intelligence

1. SUMMARY

Rationale: Fetal and neonatal alloimmune thrombocytopenia (FNAIT) is a disease caused by allo-immunisation during pregnancy. If left untreated, FNAIT can lead to severe fetal intracranial haemorrhage. This complication can be prevented by weekly administration of intravenous immunoglobulin (IVIg) to the mother during pregnancy. Although treatment with IVIg is nowadays considered as the golden standard for the management of FNAIT, the exact mechanism of action of IVIg is still under debate. Most importantly, the long-term effects and safety of IVIg treatment in FNAIT have not yet been evaluated. The use of IVIg during pregnancy for FNAIT is therefore still 'off-label'. The medication leaflet of IVIg continues to state that there is insufficient knowledge on the use of this product during pregnancy, despite all the years of experience and implementation in virtually all international guidelines.

Knowledge on long-term development of FNAIT survivors with or without IVIg treatment is very limited but an important subject in the counselling of parents of newly diagnosed cases. A greater understanding of the long-term outcome and the effects of IVIg on child development is necessary.

Objective: To evaluate the long-term neurodevelopmental outcome in two groups of children with FNAIT. First, children with unanticipated disease 'index cases' that were born without maternal IVIg administration during pregnancy. Second, children with anticipated disease; their mothers were treated with IVIg during pregnancy.

Study design: Observational cohort study.

Study population: The study population consists of two different cohorts of FNAIT children born in the Netherlands between 2002 and 2017.

- Cohort 1: The first cohort of children will consist children with unanticipated disease, 'index cases that were born without maternal IVIg administration during pregnancy.'
- Cohort 2: Second cohort will consist of children with anticipated disease; their mothers were treated with IVIg during pregnancy.

Methods: Neurodevelopmental evaluation of the children will be performed, at a minimum age of 24 months. This includes an assessment of neurologic, motor and cognitive development using standardized psychometric tests appropriate for age and parent-report questionnaires on Health Related Quality of Life (HRQoL) and behavioral functioning. Academic trajectories of FNAIT children will be assessed by collecting test scores from the Dutch pupil monitoring system. We will assess allergies and the course of infections by questionnaires.

Main study parameters/endpoints: The primary outcome is cognitive development i.e., cognitive test score or Intelligence Quotient (IQ). Secondary outcome is neurodevelopmental impairment (NDI); a composite outcome including cerebral palsy Gross Motor Functioning

Classification System (GMFCS) \geq II, cognitive and/or motor test score of less than 70 (-2 SD), hearing loss requiring amplification or visual impairment (legally certifiable as blind or partially sighted). Other secondary outcome parameters are HRQoL and behavioral functioning and the academic performance. The course and incidence of infections and allergies will be assessed.

Nature and extent of the burden and risks associated with participation, benefit and group relatedness

The burden of neurodevelopmental assessment tests is minimal (e.g. 120 minutes at 2 to 6 years and 150 minutes at 7 to 17 years follow-up). Neurodevelopmental assessment is generally experienced as enjoyable for children. Parents will complete a HRQoL- and a behavioral questionnaire for their children. Academic performance will be evaluated by scores that were obtained at school. Participation does not result in any direct benefit.

2. INTRODUCTION AND RATIONALE

Fetal and neonatal alloimmune thrombocytopenia (FNAIT) is the most common cause of thrombocytopenia in otherwise healthy term-born neonates. [1] FNAIT is a rare disease with an incidence estimated around 1 per 1000 live newborns. [2] During pregnancy alloimmunization can occur due to incompatibility of the Human Platelet Antigens (HPA) on the maternal and fetal platelets. Alloimmunization and maternal production of antibodies directed against the HPA-positive fetal platelets, leads to thrombocytopenia and an increased risk of intracranial hemorrhages (ICH) in the fetus. Clinical presentation can vary from skin bleedings to severe ICH leading to lifelong neurologic sequelae or intrauterine death. [2] [3]

In the past, FNAIT was managed with invasive and high-risk interventions including intrauterine platelet transfusion (IUPT). Since the end of the 20th century, invasive intrauterine transfusions (IUT) were replaced by a new, non-invasive therapy: maternal administration of intravenous immunoglobulin (IVIg). This novel therapy resulted in a significant lower risk of intrauterine fetal death and ICH. [4] Intervention with immune modulation in the semi -allogenic environment of the fetus by administration of immunoglobulins (Ig) is successful, especially in preventing ICH. [5] However antenatal treatment with IVIg has been implemented as standard of care without strong methodological follow-up research of children from mothers treated with IVIg. To date, only two follow-up studies have been published in children with anticipated FNAIT cases. The first study of a FNAIT cohort treated with IVIg was done by Ward et al. in 2006. [6] They concluded that development of children treated for FNAIT was better compared to their non-treated siblings. Their conclusions were based on non-validated questionnaires taken by telephone, assessing the behavioral outcome of the children and were limited by a ~40% lost-to-follow-up rate. [6] A second follow-up study including 39 children was published by a research group from our center in 2004. This research stated that the outcome in children with FNAIT and exposed to maternal IVIg treatment was similar to the normal population. However, this study included a heterogenic group of children with different treatment strategies including IUT, hampering definitive conclusions and substantiating the need for more research. [7]

No long-term standardized follow-up studies were performed on FNAIT cases without antenatal treatment and/or ICH. The natural course of the disease and long-term effects of thrombocytopenia on the developing fetus and newborn are unknown. FNAIT is defined as a disease caused by alloantibodies, resulting in thrombocytopenia and a risk of bleeding in the neonate. In the last years, evidence is increasing that the maternal alloantibodies can also bind to the fetal endothelium and may impair angiogenesis in the developing fetuses [8] [9]. It

is not known at which moment in pregnancy the developing brain is most vulnerable for damage induced by these kind of alloantibodies. The timing in fetal life FNAIT associated ICH ranges from 23 to 42 weeks [10], but small bleeding may not be diagnosed. It may also be that these type of alloantibodies not lead to ICH but to other type of cerebral damage. These lesions can remain subclinical directly after birth but lead to developmental delay on the long term. This knowledge can be of great interest when counseling parents with a risk of FNAIT or in writing guidelines.

For 3 decades a nationwide screening on FNAIT to detect pregnancies with alloantibodies in time and start treatment to prevent bleedings is being discussed. If alloantibodies lead to cerebral damage on the long term also in patients without large ICH this might have large implications in the debate on the introduction of a national screening programme. Therefore we want to underline that more knowledge about the long-term development of FNAIT survivors is required.

The Leiden University Medical Center (LUMC), a national fetal therapy center in The Netherlands, has a close and long-lasting collaboration with Sanquin. This collaboration offers a unique opportunity to evaluate a large and complete cohort of children with FNAIT. LUMC and Sanquin are both nationwide referral centers for FNAIT and committed to improve timely detection of high-risk cases who need intra-uterine therapy. In our opinion we have a duty as a national expertise center to assess long-term outcome in children with FNAIT and describe the natural history of children affected by FNAIT and the long term effects of a given therapy.

3. OBJECTIVES

3.1 Primary objective(s)

The primary objective is to determine the cognitive test score of children diagnosed with FNAIT without and with antenatal treatment. We will assess the neurodevelopmental outcome, with IQ score as outcome measure, of two groups:

Cohort 1: To evaluate the natural history of FNAIT, we will include in this first cohort all FNAIT survivors without antenatal treatment. Our hypothesis is that the cognitive test score in this cohort will be lower compared to the general population.

Cohort 2: To evaluate the safety and benefit of IVIg treatment, the IQ score in all FNAIT survivors treated with antenatal IVIg treatment will be determined. Our hypothesis is that the cognitive test score in this cohort is similar to the general population.

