5.4 Sample size calculation

Of note, performing sample size calculations in the context of this rare disease is difficult since literature is scarce and heterogeneous.

We performed two different sample size calculations for the two cohorts.

Cohort 1: Using the literature to date we estimated that the IQ score of FNAIT survivors without antenatal treatment is lower, that is 92 versus average (100) in the normal population. To show a difference in IQ score between FNAIT survivors without IVIg treatment compared to a fixed average of 100, we performed a sample size calculation for a one-sample t-test. We calculated that a minimum group size of 39 was needed to show a mean difference of 7 IQ points with a power of 0.8 and a significance of 0.05. We assume a standard deviation (SD) of 15 for the IQ score.

Cohort 2: In the FNAIT survivors with antenatal treatment we expect no difference in IQ score between cases and the national average. To show that there is no difference IQ score in anticipated IVIg treatment compared to the Dutch average we perform a non-inferiority calculation by a one-sample t-test. In this case we need a sample size of 39 children with a non-inferiority margin of 7 IQ points, with a power of 0.8 and a significance level of 0.025. We assume a standard deviation (SD) of 15 for the IQ score.

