11. STATISTICAL ANALYSIS

Continuous parametric data will be presented with mean \pm standard deviation (SD) or median with interquartile range (IQR) as appropriate. Categorical data will be presented as counts and percentages within each study group.

The cognitive test score of both cohorts will be compared with the Dutch average by using a linear regression model. The following potential confounders for cognitive development (IQ score) identified in earlier research will be used in the analysis;

- Sex
- Gestational age at birth
- Small for gestational age
- Neonatal morbidity
- Level of education of the parents

In second cohort; the FNAIT survivors with IVIg treatment atopic constitution and the course of infections will be assessed in a secondary analysis.

In the assessment of course of infections the following confounders will be used in the analysis by using a linear regression model;

- Day-care visit
- Smoking in a household
- Time of the year that the questionnaire was filled in

In the analysis of allergies and asthma the following confounders will be used in the analysis by using a linear regression model;

- Presence of a first degree family member with asthma eczema or allergy
- Smoking in a household

All data is analysed with IBM SPSS Statistics version 24 (IBM Software, NY, USA, 2016).

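### Cohort 2: Section 5.4 says a 7-point non-inferiority test will show no difference in IQ, and Section 11 does not carry that test's rule into the analysis

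*Combined protocol and SAP*

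**What the plan says.** Section 3.1 gives the reason for studying cohort 2 as follows: "To evaluate the safety and benefit of IVIg treatment, the IQ score in all FNAIT survivors treated with antenatal IVIg treatment will be determined". The hypothesis follows: "Our hypothesis is that the cognitive test score in this cohort is similar to the general population".

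Section 5.4 turns this into a test: "To show that there is no difference IQ score in anticipated IVIg treatment compared to the Dutch average we perform a non-inferiority calculation". It is to be a one-sample t-test "with a non-inferiority margin of 7 IQ points, with a power of 0.8 and a significance level of 0.025", with SD 15 and 39 children. The sidedness of the 0.025 level is not stated. For cohort 1 the same section names the reference value ("compared to a fixed average of 100"); for cohort 2 it speaks of the Dutch or national average without giving a number.

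Section 11 says of IQ: "The cognitive test score of both cohorts will be compared with the Dutch average by using a linear regression model". It then adds: "The following potential confounders for cognitive development (IQ score) identified in earlier research will be used in the analysis", and lists five: sex, gestational age at birth, small for gestational age, neonatal morbidity and parental education. Non-inferiority, the 7-point margin, the 0.025 level and a confidence limit do not appear there.

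**The concern.** Three steps that should agree do not.

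- **Claim and test.** A non-inferiority test with a 7-point margin has one bound. Passing it rules out a mean 7 or more points below the norm. It does not establish that there is no difference, which is the conclusion 5.4 attaches to it.
- **Test and analysis.** The test that was sized concerns an unadjusted one-sample mean. The analysis that is described is a covariate regression with no success criterion. A reader of Section 11 alone cannot tell what result would support the hypothesis of similarity, or on which mean.
- **Aim and comparison (secondary).** Every planned IQ comparison is of one cohort with the norm. None is with untreated children with FNAIT, so none can show that IVIg improved IQ.

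The Summary says that long-term outcome matters for counselling parents of newly diagnosed cases, and that the long-term safety of IVIg in FNAIT has not been evaluated. Whether the study can report no difference, or only a deficit of less than 7 points, therefore matters to the people it is meant to inform.

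**Working it through.** **Inputs (Section 5.4):** SD 15, margin 7, power 0.8, level 0.025, n=39, assumed true difference 0. The Dutch average is taken as 100, the value 5.4 gives for cohort 1. All figures are for an unadjusted mean, because the documents give no covariate effects.

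**1. The plan's sample size.** Normal approximation: n = [15 × (1.960 + 0.842) / 7]² = 36.04, so 37. The exact one-sample t-test (noncentral t, noncentrality 7√n/15) gives:

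- one-sided 0.025: power 0.7999 at n=38 and 0.811 at n=39, so the minimum is 39;
- 0.025 read as two-sided (0.0125 in the tail): minimum 47.

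The plan's 39 is reproduced, and the level must be one-sided.

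**2. What success means at n=39.** Standard error = 15/√39 = 2.40; t(0.975, 38 df) = 2.024; half-width of the 95% CI = 2.024 × 2.40 = 4.86. If the observed SD is 15:

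- non-inferiority is met when the observed mean exceeds 93 + 4.86 = 97.86;
- a two-sided 5% test against 100 is non-significant from 100 − 4.86 = 95.14 to 100 + 4.86 = 104.86.

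Observed means between about 95.1 and 97.9 would thus be non-significant against 100 and would also fail the 5.4 test.

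**3. Deficits that can pass the 5.4 test (n=39).**

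| True mean | P(non-inferiority met) |
|---|---|
| 93 | 0.025 |
| 96 | 0.229 |
| 98 | 0.527 |
| 100 | 0.811 |

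A pass is compatible with a real deficit of a few points, so it does not show that there is none.

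**4. Illustration: what the absent rule could cost.** Suppose non-significance on a two-sided 5% test against 100 were read as similarity. Section 11 does not state this rule. The probability of accepting a true mean of 93, a deficit equal to the margin, would be as follows. Sizes above 39 are assumed, since the documents do not give the achieved n.

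| n | Non-significance read as similar | 5.4 rule |
|---|---|---|
| 39 | 19% | 2.5% |
| 50 | 10% | 2.5% |
| 60 | 5.5% | 2.5% |
| 80 | 1.5% | 2.5% |

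The 5.4 rule holds the error at 2.5% whatever the size. The alternative depends on n: it is laxer at 39 to 60 and stricter at 80.

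**5. Crude or adjusted.** The 5.4 test concerns the plain cohort mean. In a regression with covariates, the mean set against a fixed norm depends on the covariate values at which it is evaluated. Section 11 does not give these values, nor how the Dutch average enters the model.

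**The case against.** The strongest reply is that 5.4 already discloses the operational meaning. The sentence about no difference itself names a non-inferiority calculation, and the margin, power and level follow at once. In 3.1, similarity is a hypothesis and not a conclusion to be declared. Every non-inferiority test leaves deficits smaller than its margin open. This lowers the weight of the wording point but does not remove it: the stated conclusion still does not follow from the test, and a sample-size section does not say how the final regression is to be judged.

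A reader might infer that Section 11 will treat a non-significant difference as similarity. The documents do not say so. Section 11 states no level and no such rule, and the only level and margin for cohort 2 are those in 5.4. The 19% is therefore conditional on a misreading that the text leaves open. It also belongs to n=39, while Sections 4 and 5.1 invite all eligible children born between 2002 and 2017.

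A reader might also infer that the study is misdirected because benefit cannot be shown, or that it needs a cohort 1 versus cohort 2 test. The text does not support that either. Section 3.1 opens with determining the cognitive score, the cohort 2 hypothesis concerns the general population, and 5.4 and 11 match it. Benefit is one loose word that misdirects no analysis. A contrast between the cohorts would not establish it anyway: they are non-randomised, differ as index and anticipated cases, and contain survivors only.

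Finally, Sections 3.3 and 11 plan to correct for confounding, so making the crude mean decisive would be a choice and not a correction. That stands, and the fix leaves the choice to the investigators.

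**Conclusion.** The concern holds in a limited form and should be fixed. The conclusion named in 5.4 is stronger than its test can support, and Section 11 does not specify that test. The supportable claim is that mean IQ is less than 7 points below the Dutch average. Benefit in 3.1 is a secondary wording matter.

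The only size that can be given is illustrative: acceptance of a true 7-point deficit of 19% at n=39, falling to 1.5% at n=80, against 2.5% under the 5.4 rule. It assumes SD 15, a norm of 100, an unadjusted mean and a decision rule that the plan does not contain. A reader might take the point as a challenge to the sample size; it is not, since 39 is reproduced with a one-sided level of 0.025.

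**What to change.** - **Section 5.4.** State the purpose of the cohort 2 test as showing that mean IQ is less than 7 points below the Dutch average, and that the 0.025 level is one-sided. Define similarity in **Section 3.1** in the same way. The expectation of no difference can stay as the planning assumption.
- **Section 11.** State that the cohort 2 conclusion rests on the 5.4 rule: the lower limit of the two-sided 95% CI for mean IQ lies above the Dutch average minus 7 (93 if the average is taken as 100). Add that a non-significant difference from the norm is not evidence of similarity. Say which mean the rule applies to. Section 5.4 sized the unadjusted mean; if the adjusted mean is preferred, give the covariate values at which it is evaluated.
- **Section 3.1.** Delete benefit, or state that comparison with the norm cannot establish it.

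The cost is a few sentences, with no new data and no change to n=39. The claim becomes less favourable: at a true mean of 100 and n=39, non-inferiority is shown in 81% of studies, whereas a non-significant difference would occur in 95%. The investigators must also decide in advance whether the crude or the adjusted mean is decisive. If they choose the crude mean, the planned adjustment no longer decides the result.

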3.2 Secondary Objective(s)

In both groups we will assess the incidence of neurodevelopmental impairment (NDI). NDI is a composite outcome including cerebral palsy (GMFCS \geq II), cognitive or motor test score of less than 70, hearing loss requiring amplification or visual impairment (legally certifiable as blind or partially sighted). Other secondary outcomes will be HRQoL and behavioral problem score. In both cohorts we will assess academic performance by evaluation of test scores on three domains; arithmetic and spelling performance and reading comprehension. [11-13]

We will also focus on potential long-term side effects of IVIg treatment and determine the prevalence of allergies, eczema, asthma and the course of infections.

3.3 Other study parameters

We will gather the data about the following data of our cases; age and sex of the child, obstetric medical data and neonatal characteristics and morbidity of the study population. Parents will be asked to complete a questionnaire to assess the highest level of education of the parents. We use this data to describe our study population and correct for potential confounding of these factors on neurodevelopmental outcome as described in chapter 11. Study parameters are summarized in Table 1, a list of definitions can be found in Table 3.

Possible confounding factors for allergies are the family history for asthma, allergies or eczema. For evaluation of the infections it is important to assess smoking at home and day-care visit as possible confounding factors.

Table 1: Study parameters

Study parameters		
Obstetric data	Maternal characteristics	Age mother at delivery Obstetric history Medication usage during pregnancy
	Pregnancy characteristics	Gravidity/Parity Pregnancy induced hypertension Pre-eclampsia Signs of bleeding in the fetus at ultrasound
	FNAIT related therapy	IVIg treatment Intra-uterine transfusions Treatment with corticosteroids
	Labour characteristics	Mode parturition Gestational age at delivery
	Placental features	Placenta weight
Neonatal data	Birth data	Gestational age at birth Birthweight Apgar score
	Severe neonatal morbidity	Respiratory distress syndrome Perinatal asphyxia Proven early onset neonatal sepsis Retinopathy of prematurity Necrotizing enterocolitis
	Neonatal neurologic sequelae	Intracranial haemorrhage Cystic periventricular leukomalacia Ventricular dilatation Porencephalic or parenchymal cysts Convulsions Any cerebral lesions associated with adverse neurologic outcome
	Signs of bleeding	Skin manifestations Intracerebral bleeding Organ bleeding Increased bleeding tendency, reported by the caregiver
	Therapy	Platelet transfusions IVIg treatment

Table 1: Study parameters

[figure not shown]
Study parameters		
Laboratory data	HPA	HPA incompatibility HPA genotyping Anti-HPA-titre Platelet count Directly after birth Nadir Other Presence of HLA class I antibodies
Outcome	Neurodevelopmental scores	Cognitive test score Motor test score Cerebral palsy Neurodevelopmental impairment Impaired cognitive or motor development Impaired functioning in communication Bilateral blindness Bilateral deafness Quality of life Health related quality of life score Behavior Behavioural test score Academic performance Arithmetic test score at primary school Spelling test score at primary school Reading comprehension test score at primary school Immunology Prevalence of allergies Patient reported anaphylaxis Poor control of allergic rhinitis Poor control of asthma Patient reported eczema Course and incidence of infections
Potential confounders	Demographic characteristics	Age and gender of the child Family history (first degree) of allergy, astma or eczema Highest level of education of the parents Smoking at home Day-care visit Ethnic origin of the parents

